4.3.3 Consent procedures

A study investigator and/or coordinator will obtain parental informed consent. For out-born infants whose parent(s) are not physically present, we will obtain written consent over the phone. That is, if the parent(s) are at an outside hospital, we will provide them with a copy of the consent form, either from the Transport team, or via fax. The consenting study personnel will then read through the consent form with both parents (when possible) over the phone, or in person if possible. Consent will be documented according to local and national regulations.

4.3.4 Stratification, Randomization and Masking Procedures

The DCC will provide each site pharmacy with a randomization look-up table that pairs each study ID with a treatment allocation. Randomization is stratified by site and HIE severity level. See 6.3.2.1 for definitions of “moderate” and “severe” HIE, based on modified Sarnat score. The site pharmacy will then draw up the assigned study drug dose into a syringe, based on the randomization list. The appearance of the syringes of Epo and placebo are identical, thus the bedside staff remain masked. Only the research pharmacist and DCC biostatistician will be unmasked to treatment assignment. All parents, study and clinical staff, as well as all Clinical Coordinating Center (CCC) members, will remain masked to treatment assignment throughout follow-up. To ensure balance within clinical centers, the randomization will be implemented using a randomly permuted blocks design to ensure approximate balanced assignments within site and HIE severity level. The sequence of assignments for each site and stratum will be prepared in advance by the DCC.

After all final follow-up evaluations have been completed, which may be at age 8 or older if additional funding is obtained to follow subjects beyond 24 months of age, an effort will be made to inform participating families of the completion of the study, and families will be offered an opportunity to learn the treatment group assignment for their child.

5 STUDY INTERVENTIONS

5.1 STUDY DRUG ADMINISTRATION AND DURATION

Patients will be randomized to receive either IV Epo 1000 U/kg/dose (based on birth weight), or an equal volume of IV NS. Study drug (Epo vs. NS) will be administered on study days 1, 2, 3, 4, and 7, with the

same dose/volume used for each administration. We will administer Epoetin alpha for injection (4000 U/mL), manufactured by Amgen Inc., prepared and used according to the package insert. Study drug will be infused via IV push over 1-2 minutes, followed by 1 mL normal saline flush. If an institution does not allow medications to be given to neonates via IV push, study drug may be infused via pump infusion over 5 minutes, followed by 1 mL NS flush. Potential side effects of the drug administration include introduction of infection, and bleeding from the line site. All subjects will be treated in a level III or IV neonatal intensive care unit. The initial study drug dose should be given as soon as possible after randomization and no later than 24 +2 hours of age. Each subsequent dose should be given within +/- 2 hours of the time that the first dose was given (i.e., within a 4 hour window). This window provides some flexibility so that study drug does not have to be given during change of nursing shift, or while the infant is undergoing a procedure, for example. Patients will not be kept in the hospital solely for completion the study intervention. If patients are discharged from the hospital prior to day 7, they may receive the final study drug dose on the day of discharge, provided that it given at least 20 hours following the prior dose. If the patient loses IV access prior to receiving all study drug dose(s), then the remaining dose(s) may be given SC. That is, placement of a new IV for the sole purpose of giving study drug will not be required.

5.2 HANDLING OF STUDY DRUG

Each participating hospital will order Epo 4000 unit/mL, 1-ml vials, from a commercial wholesaler. Sites will generally purchase sufficient Epo to treat 2-4 patients randomized to the Epo arm. Each participating site pharmacy will be responsible for appropriately storing, accounting for and dispensing the study drug. Pharmacy accountability will be monitored closely. The research supply of Epo will be kept separate from other commercial stocks of Epo at the participating sites. Epo or placebo will be dispensed for IV administration as a patient-specific unit-dose syringe upon receipt of an investigator-physician order for a research subject. Depending on the subject's randomized treatment assignment, the un-masked pharmacy personnel will dispense a syringe containing the prescribed dose of Epo or an equivalent volume of 0.9% Sodium Chloride for Injection, USP (NS). Both Epo and placebo syringes will be labeled, packaged, transported, stored and administered in an identical manner so as to maintain the masking. Labeling will be adapted to meet local labeling requirements, but will not un-mask the drug assignment. The site pharmacies shall maintain accountability logs for all research supplies of Epo. Accountability logs will be reviewed by the DCC.

The sites will maintain accountability logs for the Epo inventory. These logs will include the purchase date (date received), lot number, expiration date, and quantity of all Epo purchased for the trial. In addition, every dose dispensed will also be recorded in a subject-specific accountability log. The Epo lot number for each dose dispensed will be recorded the inventory balance will also be noted on the accountability log. Individual subject drug accountability logs should be sent to the HEAL financial analyst on a regular basis and these logs will be reviewed by the DCC to ensure appropriate drug administration per the randomization log.

Epoetin alfa purchased for the HEAL trial will be kept refrigerated, separate from the regular medication inventory. The refrigerator will be monitored and alarmed and will have access to emergency backup power. Epoetin alfa vials must be stored in a refrigerator between 35.6°F to 46.4°F (2°C -8°C).

Epo will be labeled with stickers marked "For Investigational Use Only". The invoices for the purchase of the Epoetin will be retained at the local site in the same manner that a study drug shipping receipt would be retained.

Epo vials must be stored in the refrigerator between 36°F to 46°F (2°C to 8°C). **Do not freeze** vials and do not use a vial of Epo that has been frozen in the past. Keep vials away from direct light. **Do not shake Epo vials.** Single use vials of Epo should be used only one time. Only one dose of study drug may be drawn up at a time.

If the wrong study drug is administered to a subject (i.e., Epo is given to a Control patient, or normal saline is given to a Treatment patient), the error should be reported in a blinded manner to the CCC as a protocol violation, and all future doses should be corrected to the original randomization assignment. The study violation must also be reported to the local IRB per institutional policy.

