7.6 PROTOCOL VIOLATION/ DEVIATION REPORTING

Protocol violations require completion of a Protocol Violation Form and notification to the CCC and DCC within 3 working days. Protocol deviations require completion of a Protocol Deviation form, and the CCC and DCC should be notified within 7 days of occurrence.

7.6.1 Protocol Violations:

- Un-masking of study personnel
- Enrollment despite meeting exclusion criteria
- Enrollment despite not meeting inclusion criteria
- Consent not obtained in accordance with IRB guidelines
- Study drug administration or dosing error (incorrect study drug administered)
- Wrong study drug dose administered (>40 units, and >10% off from specified dose [1000 units/kg birthweight])
- Study drug administered when it should have been withheld

- Open label Epo administered

7.6.2 Protocol Deviations may include the following items, among others:

- Hypothermia performed not in accordance with site's hypothermia protocol (Examples include equipment malfunction, or early discontinuation due to reclassification of a patient as mild severity (i.e., even if a site has an early exit protocol, this early exit should be reported as a protocol deviation). Reasons for early discontinuation consistent with a site's cooling protocol are not considered protocol deviations (e.g., stopping cooling for ECMO, etc.))
- First study drug dose given after 26 hours of life
- Study drug dose is given outside of prescribed time window
- Study drug dose not given
- Wrong study drug dose administered (>40 units, but ≤10% off from specified dose [1000 units/kg])
- Blood samples drawn outside of the accepted time windows
- Blood collection missed
- Blood sample not in accordance with requirements per SOP (processing error, shipping error, other)
- Urine collected outside of the accepted time windows
- Urine collection missed
- Urine sample not processed appropriately
- Lost urine or blood sample
- Day 5 Sarnat not done
- Day 5 Sarnat performed out of window
- Follow-up phone contact missed
- Follow-up performed out of window
- 24-month visit not performed before 30 months of age
- 24-month visit not performed before 36 months of age

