9.6 DATA AND SAFETY MONITORING PLAN (DSMP)

The DSMB will review the accruing data to: 1) ensure that the study is adequately enrolling; 2) to ensure that there are no serious safety concerns; and 3) to assess whether the study efficacy appears overwhelming. The DSMB will be assigned by NINDS. The research coordinator at each site will monitor each subject weekly for the presence of any complications. Serious adverse events will be brought to the attention of the DSMB, and if appropriate, the IRB, in writing. An independent medical monitor will review all cases of serious adverse events.

As part of this DSMP, we will perform continuous and interim analysis of accruing safety data. We have defined potentially treatment (Epo) related serious adverse events (SAEs) that will be monitored throughout the course of the study. Specifically, for SAEs we will compare absolute rates to expected rates based on published data for similar newborns, and will seek careful DSMB review and guidance when observed rates exceed pre-specified thresholds. In addition, at planned interim analysis we will formally compare the event rates across the two treatment groups using appropriate small sample methods such as Fisher's exact test. The DCC PI will remain masked to assignment while the study staff statistician will not.

The primary outcome of the study is a composite endpoint of mortality or NDI at 24 months of age. Therefore, monitoring the primary outcome for treatment efficacy or futility is challenging. Based on enrollment plans, the majority of patients will have been randomized by the time NDI is assessed at 24 months for any participants, and therefore we do not expect to be able to conduct a first interim analysis prior to the completion of enrollment. We expect to have the primary outcome evaluated on the first quarter of subjects (n=125) after 34 months of recruitment at which point we expect to have randomized n=450 of the total n=500 subjects (90% enrollment completed). Therefore, any actions that a DSMB might take to prevent subsequent patients from receiving an ineffective treatment (futility) or to make available a useful treatment (efficacy) will not have a direct impact on patients participating in

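### Protocol 5.2 sends subject-level drug logs that show the treatment arm to the study's financial analyst, a role that 4.3.4 does not allow to be unmasked

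*Protocol*

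**What the plan says.** Protocol 4.3.4 sets a closed list: "Only the research pharmacist and DCC biostatistician will be unmasked to treatment assignment". It adds that parents, study and clinical staff, "as well as all Clinical Coordinating Center (CCC) members, will remain masked to treatment assignment throughout follow-up". SAP 1.3 repeats both statements. Protocol 9.6 and SAP 9 draw a further line inside the coordinating center: "The DCC PI will remain masked to assignment while the study staff statistician will not".

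Protocol 5.2 describes the drug records. Besides the site inventory log, "every dose dispensed will also be recorded in a subject-specific accountability log", and "The Epo lot number for each dose dispensed will be recorded". The individual logs then leave the site: "Individual subject drug accountability logs should be sent to the HEAL financial analyst on a regular basis". The same sentence says that "these logs will be reviewed by the DCC to ensure appropriate drug administration per the randomization log".

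Protocol 7.6.1 puts un-masking of study personnel first in its list of protocol violations.

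**The concern.** A log that covers one infant and ties each dose to an Epo lot is in effect a copy of that infant's allocation. Section 5.2 sends it routinely to someone outside the two permitted roles. It states no redaction, no firewall and no affiliation for that person. If the financial analyst counts as study personnel, routine compliance with 5.2 produces an event that 7.6.1 classes as a violation.

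What is at stake is the blind. The 24-month endpoint includes a neurologic examination, a GMFCS rating and a Bayley III cognitive score. Some outcomes will be settled by a masked adjudication committee, and site investigators judge whether SAEs are related to the intervention. All of this assumes that nobody near the assessments can look up an infant's arm. Masking is meant to last throughout follow-up, and 4.3.4 foresees that final evaluations may come at age 8 or later if funding is obtained. A file of individual allocations outside the permitted roles could therefore exist for years.

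**Working it through.** The plan states no figure to reproduce here. The check sets the sections side by side.

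**1. Who may know the arm.** Protocol 4.3.4 and SAP 1.3 name two roles, the research pharmacist and the DCC biostatistician. The financial analyst is neither.

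**2. Does the log show the arm?** There are two possibilities for placebo infants, and the answer is yes in both.
- If placebo infants have individual logs, their saline doses carry no Epo lot number, so a log with an Epo lot marks an Epo infant.
- If placebo infants have no such log, the existence of a log marks an Epo infant.

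The lot-number sentence in 5.2 follows directly on the sentence about subject-specific logs, but it could be read as referring to the inventory log. That would not rescue the wording. The individual logs are to be checked against the randomization log, and that check works only if each log shows which product was dispensed.

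**3. Who receives it.** Two recipients are named.
- The financial analyst, on a regular basis. Nothing in 5.2 says that product identity is removed first.
- The DCC, without restriction to a person. Under 9.6 the DCC PI is masked and the study staff statistician is not, so the unqualified name covers both a masked and an unmasked person.

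**4. How many infants.** SAP 1.2 plans 500 / 2 = 250 infants per arm. Up to 250 of 250 Epo infants are identifiable from the logs, and the other 500 − 250 = 250 by elimination. With five doses per infant there could be up to 5 × 250 = 1,250 Epo dose entries, and one entry per infant is enough to reveal the arm.

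**5. Route from the analyst to the endpoint.** I looked for one and found none. Neither document gives the analyst outcome assessment, SAE, site-visit or adjudication duties. Equally, neither says that the analyst is kept apart from CCC or site staff.

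**The case against.** The sponsor's best answer is that the analyst is an administrator. The adjudication committee is masked (9.2.1.4), the Medical Monitor is masked (section 7), and relatedness is judged by the site investigator (7.2). The count of 250 is a ceiling on what one person could see and does not measure bias in any endpoint. All of that stands, and it limits the size of the point. It does not remove the contradiction between 4.3.4 and 5.2.

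On the DCC, the sponsor can say that only someone holding the allocation can check logs against the randomization log. Section 10.2 also makes portal access depend on role, so the unmasked statistician is the natural reader. This is a fair reading and I would not call the DCC wording a breach. It is still easy to name the person.

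A reader might go further and infer that the wrong-dose rules in 7.6 also unmask infants, because they are written in units: "Wrong study drug dose administered (>40 units, and >10% off from specified dose [1000 units/kg birthweight", with a matching deviation rule for errors within 10%. On that view saline contains no units, so the rule would catch only Epo infants, point to their arm in reports to the CCC, and distort the decision on a per-protocol analysis. The documents do not support this:
- Protocol 5.1 uses the term study drug for both Epo and saline and gives placebo in equal volume. Every infant therefore has a nominal dose in units set by birth weight, and a report in nominal units looks the same in both arms. At 4000 U/mL, 40 units is 40 / 4000 = 0.01 mL in either syringe.
- Taken literally, a saline syringe with 0 units is 100% off the specified dose, so the rule would flag every placebo dose and not exempt the arm.
- Section 9.3.6 looks at dosing and timing in general and does not cite the 7.6 limits.
- Restating the limits as volume only could lose an error that they now catch: the right volume drawn from a vial of the wrong strength.

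**Conclusion.** The contradiction is real and follows from the text alone. Section 5.2, carried out as written, shows individual allocation to a third role, while 4.3.4 and SAP 1.3 permit two. It reaches up to all 250 Epo infants and, by elimination, the placebo arm.

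The likely effect on the primary outcome is small. A reader might infer that masked adjudication or relatedness calls are compromised, but no section links the analyst to either, so the finding is a preventable masking risk and not a shown bias. The change is worth making because it protects the blind at almost no cost.

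This rests on two assumptions: that the logs are sent with product identity intact, since 5.2 mentions no redaction, and that no SOP outside these documents already separates the analyst. If such an SOP exists, the protocol only needs to say so.

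**What to change.** In Protocol 5.2, send subject-level accountability logs only to the unmasked DCC biostatistician, and name that role in both places where the section now says the DCC in general. Give the financial analyst site-level totals of vials used per period, without subject IDs. No dose, dose limit or clinical rule changes, and the wrong-dose limits in 7.6 stay as they are.

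The cost is a few words in the protocol and the pharmacy SOP, plus a short site-level cost form. The downside is that reimbursement is checked against totals, with the per-infant check left to the biostatistician. If finance cannot work from totals, the weaker alternative is to add the analyst to the unmasked list in 4.3.4 and SAP 1.3, with a stated firewall from CCC and site staff. That also reconciles the sections, but it leaves one more person holding individual allocations.

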5.3 CONCOMITANT AND REQUIRED INTERVENTIONS

Ideally, all infants enrolled in HEAL will be treated as consistently as possible across sites, so the major difference between subjects is their treatment with Epo vs. placebo. To this end, we have developed a set of recommended Clinical Guidelines regarding the treatment of infants with HIE, and sites will be encouraged to follow these guidelines when possible. These guidelines address 1) hypothermia therapy duration and goal temperature, as well as use of sedatives; 2) monitoring of laboratory tests during the neonatal period; 3) EEG brain monitoring; and 4) general approach to treatment of clinical and sub-clinical seizures.

5.4 PROHIBITED AND PRECAUTIONARY INTERVENTIONS

There are no prohibited and precautionary interventions for this study.

5.5 ADHERENCE ASSESSMENT

Study drug will be administered by a nurse (i.e., bedside nurse, charge nurse, etc.) in the neonatal intensive care unit. A detailed record of study drug administration will be kept by Investigational Drug Services Pharmacy, and documentation of study drug administration will be completed by the nurse administering the drug.

6 CLINICAL AND LABORATORY EVALUATIONS

6.1 SCHEDULE OF EVALUATIONS

Table 3. Schedule of Evaluations

Evaluation	Visit Day	Window	Location	Details
Screening	Study Day 0 or 1	Before randomization	NICU	Screening Clinical Assessment (Apgar, resuscitation, acidosis, Modified Sarnat exam, Inclusion/Exclusion assessment)
Therapeutic Hypothermia Begins	Study Day 0 or 1	Begin by <6 hours post-birth	NICU	Begins prior to administration of study drug and at <6 hours of age, continues for 72 hours, per standard of care.
Consent & Enrollment	Study Day 0 or 1	Prior to 24 + 2 hours post-birth	NICU	Informed Consent
Randomization	Study Day 0 or 1	Prior to 24 + 2 hours post-birth	Pharmacy	HEAL Portal
Blood sample (pre-intervention)	Study Day 0 or 1	Before Intervention 1	NICU	1.5 mL blood sample
Urine sample 1	Study Day 0 or 1	1 st void after consent	NICU	1-2 mL urine sample, ideally obtained prior to study drug administration (note: urine may be collected after study drug administration if not available earlier, and in this case, does not require a Protocol Deviation)
Intervention 1 (study drug)*	Study Day 1	Prior to 24 + 2 hours post-birth	NICU	Target time is as soon as possible
Intervention 2 (study drug)	Study Day 2	24 ± 2 hours following Intervention 1	NICU	Target time is same time of day as Intervention 1
Blood sample 2	Study Day 2	24 ± 2 hours following Intervention 1	NICU	1.5 mL blood sample. Target time is same time of day as Intervention 2
Intervention 3 (study drug)	Study Day 3	48 ± 2 hours following Intervention 1	NICU	Target time is same time of day as Intervention 1
Urine sample 2	Study Day 3-4	After rewarming completed, and within 24 hours after rewarming	NICU	1-2 mL urine sample

Evaluation	Visit Day	Window	Location	Details
Intervention 4 (study drug)	Study Day 4	72 ± 2 hours following Intervention 1	NICU	Target time is same time of day as Intervention 1
Blood sample 3	Study Day 4	72 ± 2 hours following Intervention 1	NICU	1.5 mL blood sample. Target time is same time of day as Intervention 4
Brain MRI/MRS (routine clinical care)	Study Day 4-5	Ideally between 96-144 hours post-birth	NICU	After rewarming, and ideally after Intervention 4 has been administered
Clinical assessment	Study Day 5	Anytime this calendar day	NICU	Modified Sarnat exam
Intervention 5 (study drug)	Study Day 7	144 ± 2 hours following Intervention 1	NICU	Target time is same time of day as Intervention 1
EEG Summary	Study Days 1-7	N/A	NICU	Upload EEG reports
Clinical Blood Test Summary	Study Days 1-7	N/A	NICU	Record renal function, CBC, liver function labs, as collected per site's clinical standard of care.
Follow-up (month 4)	Month 4	Day of month (±7 days)	Phone	Contact info, intervening medical and developmental history, assess adverse events
Follow-up (month 8)	Month 8	Day of month (±7 days)	Phone	Contact info, intervening medical and developmental history, assess adverse events
Follow-up (month 12)	Month 12	Day of month (±28 days)	Phone	Contact info, intervening medical and developmental history, WIDEA, assess adverse events
Follow-up (month 18)	Month 18	Day of month (±28 days)	Phone	Contact info, intervening medical and developmental history, WIDEA, assess adverse events
Follow-up (month 24)	Month 24	Day of month (±56 days)	Phone (may also be done in clinic)	Contact info, intervening medical and developmental history, WIDEA, assess adverse events
Follow-up (month 24)	Month 24	Day of month (±56 days, may extend up to 36 months of age in extenuating circumstances, e.g., COVID-19)	Clinic	Standard Neurologic Exam (Kuban), Bayley III, GMFCS Evaluation, Child Behavior Checklist (CBCL), growth parameters, assess adverse events

Evaluation	Visit Day	Window	Location	Details
Extended Contact Calls	Months 30, 36, 42, 48, 54, 60, 66, 72, 78, 84, 90, 96	Day of month (± 56 days)	Phone	
Confirm contact information, collect basic information about how child is doing. WIDEA at 30 and 36 months
 
Note: failure to complete, or completing these Extended Contact calls outside of window does NOT constitute a study deviation.

* Study Day 1 is defined as the calendar day on which Intervention 1 is administered. If the study drug is administered on the calendar day following the day of birth, then the day of birth will be called Study Day 0.
				

